#### **4.3 Extension period inclusion criteria**

Patients eligible for inclusion in the extension period must fulfill all the following criteria:

1. Ongoing study treatment for the randomized part of the trial at the EoT visit
2. Able to provide written informed consent to enter the extension period

#### **4.4 Extension period exclusion criteria**

Patients fulfilling any of the following criteria are not eligible for inclusion in the extension period:

1. History of hypersensitivity to abelacimab
2. Patients with an intracranial or intraocular bleed within the 3 months prior to EoT
3. Clinically significant mitral stenosis (valve area <1.5 cm^2)
4. Mechanical heart valve or other indication for anticoagulation therapy other than atrial fibrillation (e.g., venous thromboembolism)
5. Known presence of an atrial myxoma or left ventricular thrombus
6. History of left atrial appendage closure or removal
7. Active endocarditis
8. Systolic BP >180 mm Hg or diastolic BP >100 mm Hg on repeated measurements
9. Planned invasive procedure with potential for uncontrolled bleeding (e.g. major surgery)

10. Any stroke within 14 days before EoT or TIA within 3 days before EoT
11. Platelet count  $\leq 70,000/\text{mm}^3$
12. Hemoglobin  $< 8 \text{ g/dL}$
13. Women of child-bearing potential (WOCBP) as described in Section 4.2.
14. Sexually active males with female partners who are WOCBP must agree to use a condom or use other reliable birth control methods during their time in the study and should not father a child or donate sperm during the study period
15. History of drug addiction or alcohol abuse in the past 2 years, as judged by the Investigator
16. Significant illness which has not resolved within two (2) weeks prior to the EoT
17. Any medical or psychiatric condition which in the judgment of the Investigator may preclude patients of complying with study requirements for the duration of the study

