### 3.1.2 Randomization and treatment

Investigators should take measures to minimize the duration of time from when the patient is screened until determined to be eligible for randomization into the study. Eligible patients who are not on oral anticoagulation at screening should be randomized as soon as possible into the study and begin their assigned study drug on Day 1.

Patients who meet all study entry criteria but are on oral anticoagulation therapy at screening will be transitioned from their baseline anticoagulant therapy prior to being randomized and receive the first administration of study drug on Day 1 according to the guidelines in [Table 3-1](#). Similarly, patients receiving rivaroxaban in the Randomized Treatment Period and entering the

Extension Period should transition according to the guidelines in [Table 3-1](#).

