### 4.2 Exclusion criteria

Patients fulfilling any of the following criteria are not eligible for inclusion in this study:

1. Use of other investigational drugs within 5 half-lives prior to enrollment or until the expected pharmacodynamic effect has returned to baseline, whichever is longer
2. History of hypersensitivity to any of the study drugs (including rivaroxaban) or its excipients, to drugs of similar chemical classes, or any contraindication listed in the label for rivaroxaban (See [Section 6.7.1](#) for examples)
3. Patients with an intracranial or intraocular bleed within the 3 months prior to screening
4. Clinically significant mitral stenosis (valve area  $<1.5$  cm^2)
5. Mechanical heart valve or other indication for anticoagulation therapy other than atrial fibrillation (e.g., venous thromboembolism)
6. Known presence of an atrial myxoma or left ventricular thrombus
7. History of left atrial appendage closure or removal
8. Active endocarditis
9. Systolic BP  $>180$  mm Hg or diastolic BP  $>100$  mm Hg on repeated measurements at screening
10. Planned invasive procedure with potential for uncontrolled bleeding (e.g., major surgery)
11. Any stroke within 14 days before randomization or TIA within 3 days before randomization
12. A CrCl  $<15$  mL/min or on dialysis at the time of Screening
13. Platelet count  $\leq 70,000/\text{mm}^3$  at the Screening Visit
14. Hemoglobin  $<8$  g/dL at the Screening Visit
15. aPTT or PT  $>1.5$  times the upper limit of normal (ULN) at the Screening Visit, if the patient is not on an anticoagulant
16. Women of child-bearing potential (WOCBP), defined as all women physiologically capable of becoming pregnant, unless they agree to use highly effective methods of contraception during their participation in the trial and for at least 10 weeks after the last dose of abelacimab for women randomized to abelacimab. Highly effective contraception methods include:
  - Total abstinence (when this is in line with the preferred and usual lifestyle of the patient). Periodic abstinence (e.g., calendar, ovulation, symptothermal, post-ovulation methods) and withdrawal are not acceptable methods of contraception

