### 5.1 Informed consent procedures

Eligible patients may only be included in the study after providing written (witnessed, where required by law or regulation) Institutional Review Board (IRB) or Ethics Committee (EC)-approved informed consent.

Anthos Therapeutics or a delegate on their behalf will provide to investigators a proposed informed consent form (ICF) that complies with the ICH E6 Good Clinical Practice (GCP) guideline and regulatory requirements and is considered appropriate for this study. The ICF also includes a section related to optional future research which will require a separate signature if the patient agrees to future research. Any changes to the proposed consent form suggested by the Investigator must be agreed to by Anthos Therapeutics before submission to the IRB or EC.

Information about common side effects already known about the investigational drug can be found in the IB. Information about common side effects already known about rivaroxaban can be found in the Summary of Product Characteristics [Xarelto® (rivaroxaban) [SmPC](#)] and Prescribing Information [Xarelto® (rivaroxaban) – [Package Insert](#)]. This information is included in the patient informed consent and should be discussed with the patient during the study as needed. Any new information regarding the safety profile of the investigational drug that is identified between IB updates will be communicated as appropriate, for example, via an Investigator Notification or an Aggregate Safety Finding. New information which results in an update to the informed consent must be discussed with the patient.

Ensure patients are informed of the contraception requirements outlined in the [Section 4.2](#) (Exclusion criteria).

A separate optional consent form for the collection of [REDACTED] will also be offered to patients.

A copy of the approved version of all consent forms must be provided to the [REDACTED] after IRB/EC approval.

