### **6.4 Treating the patient**

#### **6.4.1 Dispensing the study drug Abelacimab**

Each study site will be supplied with abelacimab as single-use vials via the IxRS system. A unique kit number is printed on the vial label which corresponds to the abelacimab treatment

arm. Investigator staff will identify the study drug vial to be used for the patient by contacting the IxRS and obtaining the kit number containing that vial.

At the Day 1 and Day 30 visits, abelacimab will be administered to the patient by qualified medical personnel at the study center via s.c. injection as specified in the Pharmacy Manual. For these first two doses, patients must remain at the study center for at least 1 hour after administration of study drug to monitor for any ISRs, hypersensitivity reactions, or other AEs. Starting with the third dose, patients will either return to the study center every month to receive s.c. administration of study drug or opt to have study drug administered outside the study center by a visiting nurse or other assigned individual qualified to administer s.c. study medication (or a combination of visit scenarios depending on patient and site availability).

Patients participating in the extension period that received rivaroxaban or abelacimab 90 mg in the randomized period should be monitored as described above after the first dose of abelacimab 150 mg.

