### 6.7.2 Other Prohibitions and Restrictions

- Women of childbearing potential (WOCBP) must agree to remain on an effective method of contraception during their time in the study and for at least 10 weeks after the last dose of abelacimab for WOCBP randomized to abelacimab.
- Men must agree not to father a child or donate sperm during their time in the study.

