### **8.6 Pregnancy reporting**

Reproductive toxicity and teratogenicity data are not available for this antibody at this time; therefore, no guidelines on therapeutic recommendations in case of pregnancy are available.

This study enrolls women who are either of non-child-bearing potential or who have agreed to highly effective contraception as outlined in the eligibility criteria; thus pregnancy is not an expected outcome for any female study participant. However, in the case that a pregnancy in a female study participant should occur please follow the below reporting guidelines. The appropriate clinical follow-up for this patient and for the fetus is at the discretion of the Investigator.

To ensure patient safety, each pregnancy occurring after signing the informed consent must be reported to [REDACTED] within 24 hours of learning of its occurrence. The pregnancy should be followed up to determine outcome, including spontaneous or voluntary termination, details of the birth, and the presence or absence of any birth defects, congenital abnormalities, or maternal and/or newborn complications.

Pregnancy must be recorded on the Pharmacovigilance Pregnancy Form and reported by the Investigator to the [REDACTED] department. Pregnancy follow-up should be recorded on the same form and should include an assessment of the possible relationship to the study treatment.

Any SAE experienced during the pregnancy and unrelated to the pregnancy must be reported on a SAE form.

If the Investigator becomes aware of a pregnancy occurring in the partner of a subject participating in the study, the pregnancy should be reported to [REDACTED] within 24 hours of becoming aware, using Pregnancy Report Form. Information regarding the pregnant partner must only be submitted after obtaining written consent from the pregnant partner. The pregnancy should be followed up to determine outcome, including spontaneous or voluntary termination, details of the birth, and the presence or absence of any birth defects, congenital abnormalities, or maternal and/or newborn complications.

All assessments that are considered as a risk during pregnancy must not be performed, such as venography. The patient may continue all other protocol assessments.

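### The 10-week post-dose contraception rule follows randomized arm, not exposure, so it misses rivaroxaban-randomized women given abelacimab in the extension, unless Section 4.4 #13 bars all women of child-bearing potential

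*Protocol*

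**What the plan says.** Two sections of the protocol set the post-dose contraception period, and both restrict it by allocation. Section 4.2, exclusion 16, requires it "for at least 10 weeks after the last dose of abelacimab for women randomized to abelacimab". Section 6.7.2 repeats it: "for at least 10 weeks after the last dose of abelacimab for WOCBP randomized to abelacimab". The duty to use contraception while taking part in the study has no arm restriction in either place.

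The extension gives open-label abelacimab to all qualifying patients (Section 3.1), and no re-randomization is described. Rivaroxaban patients can enter it. Section 3.1.2 applies the Table 3-1 transition rules to them ("Similarly, patients receiving rivaroxaban in the Randomized Treatment Period and entering the" extension). Section 6.4.1 says that those who "received rivaroxaban or abelacimab 90 mg in the randomized period should be monitored as described above after the first dose of abelacimab 150 mg".

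The extension has its own entry criteria. Section 4.3 asks that patients be "Able to provide written informed consent to enter the extension period". Section 4.4 #13 lists as an exclusion "Women of child-bearing potential (WOCBP) as described in Section 4.2" and adds nothing about a post-dose period.

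Two other statements bear on the point. Section 8.6 records that "Reproductive toxicity and teratogenicity data are not available for this antibody at this time". Section 5.1 instructs sites: "Ensure patients are informed of the contraception requirements outlined in the" Section 4.2 criteria.

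**The concern.** The reason for a post-dose contraception period is exposure to the antibody. As worded, the period depends on the arm assigned at randomization. A woman randomized to rivaroxaban who then takes abelacimab 150 mg in the extension has never been randomized to abelacimab, so neither statement of the rule reaches her. Two women with the same extension exposure could therefore carry different duties after their last dose.

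The matter is one of participant protection. The sponsor chose at least 10 weeks while reproductive toxicity data were lacking, and sites are directed to convey the Section 4.2 wording to patients.

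**Working it through.** **Step 1. Who is covered, on the text**

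| Woman of child-bearing potential | Contraception during participation | 10 weeks after last abelacimab dose |
|---|---|---|
| Randomized to abelacimab | Yes (4.2, 6.7.2) | Yes (4.2, 6.7.2) |
| Randomized to rivaroxaban, no extension | Yes | Not needed |
| Randomized to rivaroxaban, abelacimab in the extension | Yes, if admitted | Not stated in any readable section |

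**Step 2. Whether the third row can occur**

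This depends on Section 4.4 #13.

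- *Reading A:* it imports exclusion 16 as a whole, including the exception for women who agree to contraception. The limit to women randomized to abelacimab comes with it, and the gap exists.
- *Reading B:* it borrows only the definition of child-bearing potential and excludes all such women. The row is empty and there is no gap.

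**Step 3. Size of the gap under reading A, scheduled path**

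Inputs:

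- Required period: 10 weeks × 7 = 70 days after the last dose (4.2, 6.7.2).
- Last injection to end-of-extension (EoE) visit: about 30 days (7.1). This is written for patients assigned to an abelacimab arm and is assumed to apply to her.
- EoE to end-of-study (EoS) visit: approximately 4 weeks (7.1), with a minimum of 4 weeks after EoE or after the start of standard-of-care anticoagulation, whichever is longer (3.1.4).
- End of participation: the EoS visit, which 7.1 describes as the check before patients conclude their participation.

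The whichever-is-longer clause does not move the minimum when Table 7-1 is followed:

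- A direct oral anticoagulant starts on the EoE day, so its minimum is EoE + 28.
- A vitamin K antagonist starts 3 to 5 days before the visit, so start + 28 is EoE + 23 to EoE + 25, earlier than EoE + 28. That row of Table 7-1 names only the end-of-treatment visit; the same timing is assumed for EoE.

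Shortfall = 70 − (30 + days from EoE to EoS), not below 0:

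| Days from EoE to EoS | Participation ends, days after last dose | Shortfall, days |
|---|---|---|
| 28 | 30 + 28 = 58 | 70 − 58 = 12 |
| 35 | 30 + 35 = 65 | 70 − 65 = 5 |
| 40 or more | 70 or more | 0 |

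**Step 4. Early discontinuation in the extension**

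No firm figure can be given. Section 6.6 ties the end of participation to the end of the randomized period, which is already over for an extension patient.

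**The case against.** The strongest counter-argument is that reading B is the literal one. Section 4.4 is a list of exclusions, #13 names women of child-bearing potential, and Section 4.2 contains a definition of that term for #13 to borrow. Item #14 spells out the agreement required of men, while #13 contains no such condition. This reading is possible and would close the gap. It is not the better one. Item #13 points back to a criterion that itself admits women who agree to contraception. Item #14 shows that this exclusion list is used to state contraception agreements. Section 8.6 describes the study as enrolling women who have agreed to contraception. Outright exclusion would also remove women already taking abelacimab with contraception, and no reason for that is given.

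A second objection is that the missing duty may stand where it cannot be read: the redacted lines of Section 3.1.3, Table 16-3 or the extension consent form. That is a fair limit on the claim, which cannot be that the duty is absent from the whole plan. Even so, those pages would not alter the limit stated in Sections 4.2 and 6.7.2. If the duty does appear elsewhere, these two sections need to be brought into line with it.

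The third objection is size, and it stands. Contraception applies through EoS, 12 days is the ceiling of the scheduled-path shortfall, and pregnancies are reportable in any arm. The woman concerned must be at least 55, still of child-bearing potential under the amenorrhea and hormone-level rule, randomized to rivaroxaban and on treatment at the end of the randomized period. The extension opens only after an early stop favoring abelacimab, and only at sites that choose to take part. The documents do not show that any such woman exists.

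**Conclusion.** The concern holds as stated, as a minor point. In the readable text, a safety rule meant to follow abelacimab exposure follows randomized allocation, and it omits rivaroxaban-randomized women treated in the extension unless Section 4.4 #13 excludes them all. Under that exclusion there is no gap.

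Otherwise the scheduled shortfall is 0 to 12 days out of 70. That range assumes that the Section 7.1 visit timing applies to a patient who switched from rivaroxaban and that the vitamin K antagonist row of Table 7-1 applies at EoE. Very few women could be affected, and nothing in the statistical analysis depends on it.

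**What to change.** In Section 4.2 #16 and Section 6.7.2, replace *randomized to abelacimab* with *who receive abelacimab in the randomized or extension period*. Under reading A, this takes a rivaroxaban-randomized woman in the extension from about 58 days at the scheduled minimum to the full 70, a gain of up to 12 days.

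The sponsor should also state in Section 4.4 #13 whether women of child-bearing potential are excluded outright or may enter if they agree to the Section 4.2 requirements, and should check that the extension consent form matches.

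The cost is a wording change in two places, one clarification and one document check. No visit or procedure is added.

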## 5 Procedures and assessments

Patients should be seen for all visits/assessments as outlined in the Assessment Schedule ([Appendix 3](#)) within the permitted visit windows. All randomized patients will be followed until the EoS visit, even if they prematurely discontinued study drug (see [Section 6.5](#)).

### 5.1 Informed consent procedures

Eligible patients may only be included in the study after providing written (witnessed, where required by law or regulation) Institutional Review Board (IRB) or Ethics Committee (EC)-approved informed consent.

Anthos Therapeutics or a delegate on their behalf will provide to investigators a proposed informed consent form (ICF) that complies with the ICH E6 Good Clinical Practice (GCP) guideline and regulatory requirements and is considered appropriate for this study. The ICF also includes a section related to optional future research which will require a separate signature if the patient agrees to future research. Any changes to the proposed consent form suggested by the Investigator must be agreed to by Anthos Therapeutics before submission to the IRB or EC.

Information about common side effects already known about the investigational drug can be found in the IB. Information about common side effects already known about rivaroxaban can be found in the Summary of Product Characteristics [Xarelto® (rivaroxaban) [SmPC](#)] and Prescribing Information [Xarelto® (rivaroxaban) – [Package Insert](#)]. This information is included in the patient informed consent and should be discussed with the patient during the study as needed. Any new information regarding the safety profile of the investigational drug that is identified between IB updates will be communicated as appropriate, for example, via an Investigator Notification or an Aggregate Safety Finding. New information which results in an update to the informed consent must be discussed with the patient.

Ensure patients are informed of the contraception requirements outlined in the [Section 4.2](#) (Exclusion criteria).

A separate optional consent form for the collection of [REDACTED] will also be offered to patients.

A copy of the approved version of all consent forms must be provided to the [REDACTED] after IRB/EC approval.

## 5.2 Patient screening

During the screening period, patients will undergo a medical history and physical examination including collection of vital signs and a 12-lead ECG. Blood and urine samples will be taken for clinical laboratory testing and other screening assessments. If a screening laboratory result is outside eligibility requirements, those laboratory tests which did not meet eligibility criteria may be re-tested. All results must be available prior to randomization for the patient to be enrolled in the study.

In general, it is permissible to re-screen a patient if s/he fails the initial Screening or falls out of the screening window timelines. A new screening number will be assigned to a patient who is re-screened, thus no screening number will be used twice. Re-testing of laboratory tests, which did not meet eligibility criteria, within the screening window does not constitute re-screening as it is permitted within a screening window.

Reasons for screen failure will be documented in the site log. Additionally, demographic data, reason for screen failure (inclusion/exclusion) and serious adverse event (SAE) data - as applicable - will be collected in the clinical database from patients who are considered screen failures. Adverse events from screen failures, which are not considered to be SAEs, will be followed by the investigator and collected only in the source data.

For any questions about patient eligibility or screening procedures, the investigator is encouraged to contact [REDACTED] [REDACTED]  
[REDACTED]

### 5.2.1 Patient demographics/other baseline characteristics

Demographic and baseline characteristic data will be collected on all randomized patients. Relevant medical history/current medical conditions and concomitant medications present before signing of the informed consent will also be recorded.

Investigators have the discretion to record abnormal test findings on the medical history electronic case report form (eCRF), if in their judgment, the test abnormality was present prior to the informed consent signature.

Baseline CHA2DS2-VASc score components and anticoagulant-naïve status will be collected in the clinical database. For the purposes of this study, a patient will be considered anticoagulant-naïve if, in their medical history, they have not been treated with anticoagulant therapy, e.g., VKA, DOAC, or parenteral anticoagulant therapy, for more than 60 continuous days at any time.

### 5.2.2 Height and weight

Height in centimeters (cm) and body weight [to the nearest 0.1 kilogram (kg) in indoor clothing, but without shoes] will be measured as part of the physical examination at the screening visit.

BMI will be calculated by the EDC system using the following formula:

$$\text{BMI} = \text{Body weight (kg)} / [\text{Height (m)}]^2$$

BMI results will be documented in the eCRF to 2 decimal places.

